10.7.4 Causal Relationship of Adverse Events to Rucaparib

Medical judgment should be used to determine the cause of the AE considering all relevant factors such as, but not limited to, the underlying study indication, coexisting disease, concomitant medication, relevant history, pattern of the AE, temporal relationship to the study medication, and dechallenge or rechallenge with rucaparib.

Not Related to Rucaparib	
• An AE that is clearly due to extraneous causes (eg, concurrent disease, concomitant medications, disease under study, etc.)• It does not follow a reasonable temporal sequence from administration of rucaparib• It does not follow a known pattern of response to rucaparib• It does not reappear or worsen when rucaparib is restarted, or• An alternative explanation is likely, but not clearly identifiable.
Related to Rucaparib	
• An AE that is difficult to assign to alternative causes• It follows a strong or reasonable temporal sequence from administration of rucaparib• It could not be reasonably explained by the patient’s clinical state, concurrent disease, or other concomitant therapy administered to the patient• It follows a known response pattern to rucaparib, or• It is confirmed with a positive rechallenge or supporting laboratory data.

10.8 Follow-up of Adverse Events, Serious Adverse Events, and Adverse Events of Special Interest

All AEs (including SAEs and AESIs) occurring during the study are to be followed up in accordance with good medical practice until resolved; judged no longer clinically significant; or, if a chronic condition, until fully characterized through 28 days after the last dose of study drug. Any SAEs, AESIs, and treatment-related Grade 3/4 AEs must be followed until resolution or stabilization, death, or until lost to follow-up. After the 28-day window, only SAEs considered as potentially related to rucaparib (including serious reports of pneumonitis or associated events, if considered to be related to rucaparib), and AESIs of MDS and AML, irrespective of causality, should be reported.

10.9 Potential Drug-induced Liver Injury

Wherever possible, timely confirmation of initial liver-related laboratory abnormalities should occur prior to the reporting of a potential DILI event. All occurrences of potential DILIs, meeting the defined criteria (see [Section 7.4.2](#)),⁴⁵ must be reported as SAEs (see [Section 10.7](#) for reporting details).

10.10 Regulatory Aspects of Serious Adverse Event and Adverse Events of Special Interest Reporting

It is important that the investigator provide an assessment of relationship of the SAE or AESI to study treatment at the time of the initial report. For reporting SAEs/AESIs or pregnancies, use the applicable report forms. The contact information for reporting of SAEs/AESIs or pregnancies can be found on each of the forms.

The sponsor or its designee is responsible for submitting reports of AEs associated with the use of the drug that are both serious and unexpected to the U.S. Food and Drug Administration (FDA), according to 21 Code of Federal Regulations (CFR) 312.32; to the European regulatory authorities according to the European Commission Clinical Trials Directive (2001/20/EC); and to other applicable regulatory authorities, according to national law and/or local regulations. All investigators participating in ongoing clinical studies with the study medication will receive copies of these reports for prompt submission to their IRB or IEC. In accordance with the European Commission Clinical Trials Directive (2001/20/EC), the sponsor or its designee will notify the relevant ethics committees in concerned member states of applicable suspected unexpected serious adverse reactions (SUSARs) as individual notifications or through periodic line listings.

The sponsor or its designee will submit all safety updates and periodic reports to the regulatory authorities as required by applicable regulatory requirements.

11 PLANNED STATISTICAL METHODS

11.1 General Considerations

Efficacy analyses will be presented separately for each Cohort and, if applicable, cohorts may be combined. Safety analyses will be presented separately for each Cohort and also combined for all patients who received at least one dose of protocol-specified treatment.

Quantitative variables will typically be summarized using frequencies and percentages for appropriate categorizations and may also be summarized using descriptive statistics. For variables summarized with descriptive statistics, the following will be presented: N, mean, standard deviation, median, minimum, and maximum. Categorical variables will be presented using frequencies and percentages.

The Kaplan-Meier methodology will be used to summarize time-to-event variables. If estimable, the 25th, 50th (median), and 75th percentiles with the 95% confidence interval will be summarized.

The number of patients with events and the number of censored patients will also be presented.

Further details to describe handling of missing, unused, and spurious data will be in the Statistical Analysis Plan (SAP). Unless otherwise specified, baseline is defined as the last measurement on or prior to the first day of study drug administration.

All statistical analyses will be conducted with the SAS[®] System, Version 9.3 or higher. Further details around the statistical analyses planned in this study will be outlined in the SAP. Changes to or deviations from the SAP will be described in the clinical study report (CSR).

11.2 Determination of Sample Size

The enrollment planned for this study is approximately 360 patients, with up to approximately 150 patients in Cohort A with measurable visceral and/or nodal disease (ie, up to 100 patients with a deleterious BRCA1/2 mutation [with a maximum of 60 patients who have only measurable lymph node disease], and up to approximately 50 patients with a deleterious ATM mutation), up to approximately 150 patients in Cohort B (ie, up to approximately 100 patients with a deleterious BRCA1/2 mutation and 50 patients with a deleterious ATM mutation), and up to approximately 60 patients in Cohort C.

Cohort A

Cohort A will be divided into 2 sub-cohorts defined by deleterious gene mutation (BRCA1/2 vs. ATM).

Cohort A (BRCA1/2)

A Simon 2-stage design to evaluate confirmed ORR by modified RECIST Version 1.1 criteria per investigator will be used. Characteristics of the Simon 2-stage design include:

- 5% probability of accepting a minimally effective drug
- 90% probability of accepting an effective drug
- ORR of 20% for a minimally effective drug
- ORR of 35% for an effective drug

In the first stage, 37 patients with a deleterious BRCA1/2 mutation will be evaluated. If the study is to proceed to the second stage, additional patients with a deleterious BRCA1/2 mutation will be accrued for a total of 83.

Note: If the study is to proceed to Stage 2, additional patients with a deleterious BRCA1/2 mutation up to 100 total patients (and a maximum of 60 patients with only measurable lymph node disease) will be enrolled in Cohort A (BRCA1/2) if additional clinical data is requested by the regulatory authorities to support regulatory filing. If sufficient evidence exists to support a regulatory filing prior to fully enrolling Cohort A (BRCA1/2), enrollment may be discontinued early.

Cohort A (ATM)

Patients in Cohort A (ATM), having a deleterious ATM mutation, will be enrolled concurrently with patients from Cohort A (BRCA1/2). It is expected that about 1/3 of the Cohort A patients will have deleterious ATM mutations. If 100 patients are enrolled in Cohort A (BRCA1/2), then approximately 50 patients would be expected to enroll into Cohort A (ATM).

A Simon 2-stage design to evaluate confirmed ORR by modified RECIST Version 1.1 criteria per investigator will be used. Characteristics of the Simon 2-stage (minimax) design include:

- 5% probability of accepting a minimally effective drug
- 80% probability of accepting an effective drug
- ORR of 20% for a minimally effective drug
- ORR of 35% for an effective drug

In the first stage, 31 patients with a deleterious ATM mutation will be evaluated. If the study is to proceed to the second stage, additional patients with a deleterious ATM mutation will be accrued for a total of 53.

Cohort B

Cohort B will be divided into 2 sub-cohorts defined by deleterious gene mutation (BRCA1/2 vs. ATM). Cohort B will be enrolled concurrently with Cohort A and is expected to enroll at approximately the same rate as Cohort A. Enrollment in Cohort B will be halted when Cohort A (BRCA1/2) is fully enrolled.

Cohort B (BRCA1/2)

A Simon 2-stage type futility rule will be employed in Cohort B (BRCA1/2). Characteristics of the Simon 2-stage design include:

- 5% probability of accepting a minimally effective drug
- 90% probability of accepting an effective drug
- ORR of 20% for a minimally effective drug
- ORR of 40% for an effective drug

In the first stage, 19 patients with a deleterious BRCA1/2 mutation will be evaluated. If the study is to proceed to the second stage, additional patients with a deleterious BRCA1/2 mutation will be accrued for a total of 54. Additionally, if the criteria for Stage 2 are met, additional patients, up to approximately 100 total, may be enrolled. Enrollment in Cohort B (BRCA1/2) will be halted when Cohort A (BRCA1/2) is fully enrolled.

Cohort B (ATM)

Patients in Cohort B (ATM), having a deleterious ATM mutation, will be enrolled concurrently with patients from Cohort B (BRCA1/2). It is expected that about 1/3 of the Cohort B patients will have deleterious ATM mutations. If 100 patients are enrolled in Cohort B (BRCA1/2), then approximately 50 patients would be expected to enroll into Cohort B (ATM).

A Simon 2-stage type futility rule will be employed. Characteristics of the Simon 2-stage (minimax) design include:

- 5% probability of accepting a minimally effective drug
- 80% probability of accepting an effective drug
- ORR of 20% for a minimally effective drug
- ORR of 40% for an effective drug

In the first stage, 18 patients with a deleterious ATM mutation will be evaluated. If the study is to proceed to the second stage, additional patients with a deleterious ATM mutation will be accrued for a total of 33. Additionally, if the criteria for Stage 2 are met, additional patients, up to approximately 50 total, may be enrolled. Enrollment in Cohort B (ATM) will be halted when Cohort A (BRCA1/2) is fully enrolled.

Cohort C

Up to approximately 60 patients will be enrolled into Cohort C. Enrollment in Cohort C will be halted when Cohort A (BRCA1/2) is fully enrolled. Since this cohort will enroll patients that have 1 of several different deleterious HRR gene mutations, each gene will be examined separately.

11.3 Analysis Populations

The following analysis populations are defined for the study:

Safety Population – The safety population will consist of all patients who received at least 1 dose of protocol-specified treatment.

IRR Efficacy Population – The IRR efficacy population will consist of all patients evaluable for response by RECIST Version 1.1/PCWG3 criteria ([Appendix 2](#)) per independent radiology review or, for Cohort B, PSA response.

Investigator Efficacy Population – The investigator efficacy population will consist of all patients evaluable for response by RECIST Version 1.1/PCWG3 criteria ([Appendix 2](#)) per investigator or, for Cohort B, PSA response.

Patient disposition will be summarized using frequency counts and the corresponding percentages. The number of patients in each analysis population, number of patients discontinued, and the primary reason for discontinuation will be summarized.

11.4 Demographics and Baseline Characteristics

All demographic (eg, age, race, and ethnicity as allowed by local regulations) and baseline characteristics will be summarized for the safety population.

The following baseline variables will be summarized with frequency tabulations:

- Time since diagnosis of primary tumor (months): 0 to 12, > 12 to 24, > 24;
- The following BRCA/ATM/other HRR gene mutation characteristics will also be summarized:
 - BRCA/ATM/other HRR gene mutation status (germline or somatic)

Descriptive statistics may also be used to summarize the continuous variables.

11.5 Efficacy Analyses

11.5.1 Primary Efficacy Analyses

For Cohort A, the primary efficacy endpoint for the study is confirmed radiologic ORR (CR or PR per modified RECIST Version 1.1 criteria and no bone progression per PCWG3 prior to a CR or PR) by central independent radiology review (IRR) in patients with measurable visceral and/or nodal disease at baseline per IRR (Cohort A). This endpoint will be summarized along with a 95% confidence interval and will be analyzed separately for patients with deleterious BRCA1/2 and ATM mutations.

An analysis of confirmed radiologic ORR by the investigator will also be conducted as supportive to the primary endpoint.

For Cohort B, the primary efficacy endpoint is confirmed PSA response ($\geq 50\%$ decrease) as assessed by a local laboratory in patients with non-measurable disease and will be summarized along with a 95% confidence interval and will be analyzed separately for patients with deleterious BRCA1/2 and ATM mutations.

For Cohort C, the primary endpoint is confirmed radiologic ORR if measurable visceral and/or nodal disease is present at baseline or $\geq 50\%$ PSA decrease from baseline if visceral and/or nodal disease is absent. For patients with measurable disease, response will be assessed by central IRR.

11.5.2 Secondary Efficacy Analysis

Duration of confirmed response is defined as the time from the date that a response (modified RECIST 1.1 or PSA $\geq 50\%$) is first reported to the time that progression is first documented:

- For responses per RECIST 1.1, duration of confirmed response is defined as the time from the date that a response (modified RECIST 1.1) is first reported to the time that progression (per modified RECIST Version 1.1 criteria or bone progression per PCWG3) is first documented
- For PSA-response, duration of confirmed response is defined as the time from the date that a response (PSA decrease $\geq 50\%$) is first reported to the time that PSA progression is first documented

Radiologic PFS (rPFS) is defined as the time from first dose of rucaparib to the date of first objective evidence of radiographic progression (soft tissue or bone lesion) or death due to any cause, whichever occurs first. Radiographic disease progression includes confirmed bone disease progression and soft tissue disease progression adjudicated by independent central radiological review using the PCWG3 guidelines for bone disease and modified RECIST Version 1.1 for soft tissue disease.

OS is defined as the date from first dose of rucaparib to the date of death due to any cause.

Clinical benefit rate (CBR) is defined as the combination of CR, PR, and SD as defined by modified RECIST Version 1.1 and no progression in bone by PCWG3 criteria. Per RECIST, to be assigned a best overall response of CR or PR, changes in tumor measurements must be confirmed by repeat assessments that should be performed no less than 4 weeks after the criteria for response are first met.

Confirmed PSA response is defined as $\geq 50\%$ reduction in PSA from baseline to lowest post-baseline PSA result, with a consecutive assessment conducted at least 3 weeks later. PSA response will be calculated for all patients with PSA values at baseline and at least 1 post-baseline assessment. PSA will be assessed by a local laboratory.

Similarly, PSA response will also be define as $\geq 90\%$ reduction in PSA from baseline to lowest post-baseline PSA result, with a consecutive assessment conducted at least 3 weeks later.

Time to PSA progression is defined as the time from first dose of rucaparib to the date that a $\geq 25\%$ increase and absolute increase of ≥ 2 ng/mL above the nadir (or baseline value for patients who did not have a decline in PSA) in PSA was measured. The increase must be confirmed by a second consecutive assessment conducted at least 3 weeks later.

11.5.3 Exploratory Efficacy Analyses

The endpoints for exploratory analyses are:

- To evaluate PRO using the EuroQol 5 dimensions 5 level questionnaire (EQ-5D-5L), Functional Assessment of Cancer Therapy – Prostate (FACT-P), analgesic drug score, and Brief Pain Inventory – Short Form (BPI-SF)
- To assess changes in the molecular profile over time of matched pre- and post-treatment tumor or plasma samples
- To assess concordance in HRR gene mutation status in matched Pre-Screening biopsy tissue, archival primary and metastatic tumor tissue and plasma ctDNA
- To assess ctDNA as a molecular marker of response
- To assess time to first subsequent antineoplastic therapy
- To evaluate loss of heterozygosity (LOH) in metastatic disease site biopsy and archival primary and metastatic tumor tissue samples.
- To evaluate mechanisms of response and resistance in ctDNA and progression tumor tissue samples.

11.5.3.1 Patient-reported Outcome

Patient reported outcome endpoints by FACT-P and BPI-SF will be summarized according to their respective scoring manuals. Analgesic drug score will be recorded according to the World Health Organization (WHO) scale (0 for no medication, 1 for non-opioid pain medication, 2 for opioids for moderate pain, and 3 for opioids for severe pain).

Analyses of change and/or percent change from baseline will be analyzed for each scheduled post-baseline visit and for the final visit for the EQ-5D-5L instrument and the EQ VAS. Patients who do not have both a baseline measurement and at least one post-baseline measurement will not be included.

11.5.3.2 Concordance of HRR Gene Status between Metastatic Disease Site Biopsy, Archival Primary and Metastatic Tumor Tissue, and Plasma ctDNA

Pairwise comparisons will be performed for HRR genotyping results between centrally-assessed Pre-Screening biopsy tissue, archival primary and metastatic tumor tissue (where available), and plasma ctDNA in all combinations. In particular, the concordance of genotyping results between archival primary or metastatic tissue and Pre-Screening biopsy tissue will be assessed to explore whether the HRR gene status of the archival primary or metastatic specimen accurately reflects

that found in a Pre-Screening tissue biopsy. Additionally, the sensitivity and specificity of plasma HRR gene assessment relative to the tissue results will be explored.

11.5.3.3 Changes in Tumor Samples and Changes in Circulating Tumor DNA

Changes in the molecular profile over time of matched pairs of pre and post-treatment tumor tissue (if available) and plasma will be evaluated. Additionally, analysis of ctDNA from serially collected blood will be performed to assess early changes in ctDNA that may associate with response to rucaparib, and to identify and characterize the emergence of mechanisms of resistance. The analysis will include but not be limited to reversions in HRR genes that restore wild-type function and mutations in other components of DNA repair and oncogenic signaling pathways.

Plasma and tumor samples may be used for the development of a blood or tissue-based diagnostic test.

Analyses may be performed on a subset of patients if it becomes clear that the analysis will have limited scientific value in some patients (eg, because of very low titer of ctDNA from plasma or low tumor cellularity in tumor samples), or if there are not enough serially collected blood samples from individual patients to allow for adequate biomarker evaluation.

11.5.3.4 Time to First Subsequent Antineoplastic Therapy

Time to first subsequent antineoplastic therapy will be summarized using a Kaplan-Meier plot and descriptive statistics.

11.5.3.5 Loss of Heterozygosity (LOH)

Metastatic disease site biopsy and archival primary and metastatic tumor tissue samples, where available, will be analyzed and assigned a percentage loss of heterozygosity (% LOH) score. The concordance between % LOH in archival primary and metastatic tumor tissue and screening biopsy tissue will be evaluated, and the relationship between %LOH (treated as a binary variable) and response to rucaparib will be explored

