Safety and tolerability will be assessed based on the following:

- Incidence, type, seriousness, and severity of AEs reported;
- Clinical laboratory investigations (hematology, serum chemistry, urinalysis);
- Vital signs (blood pressure, heart rate, and body temperature);
- 12-lead ECGs;
- Physical examinations; and
- ECOG performance status.

Statistical Methods

Sample Size Justification and Interim Analysis

The enrollment planned for this study is approximately 360 patients, with up to approximately 150 patients in Cohort A with measurable visceral and/or nodal disease (ie, up to 100 patients with a deleterious BRCA1/2 mutation [with a maximum of 60 patients who have only measurable lymph node disease], and up to approximately 50 patients with a deleterious ATM mutation), up to approximately 150 patients in Cohort B (ie, up to approximately 100 patients with a deleterious BRCA1/2 mutation and 50 patients with a deleterious ATM mutation), and up to approximately 60 patients in Cohort C.

Cohort A

Cohort A will be divided into 2 sub-cohorts defined by deleterious gene mutation (BRCA1/2 vs. ATM).

Cohort A (BRCA1/2)

A Simon 2-stage design to evaluate confirmed ORR by modified RECIST Version 1.1 criteria per investigator will be used. With rolling enrollment, after the first 37 patients with a deleterious BRCA1/2 mutation have either: a) completed 16 weeks of treatment or b) discontinued treatment prior to completing, an interim analysis will be performed (ie, Stage 1). If $\leq 8/37$ patients in Stage 1 have a confirmed objective response (CR or PR per

investigator and without progression in bone per PCWG3), the DMC will evaluate the overall benefit/risk for patients with deleterious BRCA1/2 mutations in this cohort and make a recommendation whether further enrollment should be discontinued. If $\geq 9/37$ patients have a confirmed objective response, then enrollment will continue with additional patients in Stage 2. With 83 total patients with a deleterious BRCA1/2 mutation, characteristics of the Simon 2-stage design include:

- 5% probability of accepting a minimally effective drug
- 90% probability of accepting an effective drug
- ORR of 20% for a minimally effective drug
- ORR of 35% for an effective drug

If there are at least 23 responses in 83 patients with a deleterious BRCA1/2 mutation, the null hypothesis (ORR = 20%) will be rejected. This design yields a type I error rate of 5% and power of 90% when the true response rate is 35%.

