10.3.6 Genomic Loss of Heterozygosity (%LOH)

The percentage genomic loss of heterozygosity (% LOH) will be determined from all tissue samples with adequate sequencing data. The concordance between % LOH in archival and metastatic samples will be evaluated. The relationship between % LOH and response to rucaparib may also be explored.

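### Protocol 11.5.3.5 relates response to a dichotomised %LOH with no stated cut-point; SAP 10.3.6 drops the dichotomy without naming a form; the SAP should specify a continuous analysis.

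*Protocol*

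**What the plan says.** Evaluation of LOH in tumour tissue is an exploratory objective (Protocol 4.3). Under Protocol 11.5.3.5, samples "will be analyzed and assigned a percentage loss of heterozygosity (% LOH) score", concordance between tissue types is examined, and then "the relationship between %LOH (treated as a binary variable) and response to rucaparib will be explored". No threshold follows, and no criterion for one is cited.

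SAP 10.3.6 says %LOH "will be determined from all tissue samples with adequate sequencing data" and, on response, only this: "The relationship between % LOH and response to rucaparib may also be explored". The binary treatment is absent, a firm intention has become optional, and no model, variable form or cut-point is given. SAP Table 1 lists concordance as the only LOH endpoint. SAP Section 13 records changes to PSA response, PSA progression, clinical benefit rate, the PSA waterfall plot and the CTCAE version. It records nothing on LOH.

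The number of patients who will have a score is not stated. The protocol restricts the analysis to samples that are available, and the SAP to those with adequate sequencing data.

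**The concern.** A percentage score orders patients along a scale. Splitting it treats everyone on one side of the cut as alike and discards that ordering. If response changes gradually with LOH, this wastes information in an analysis already limited to patients with usable tissue.

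The other dichotomies in the plan are defined. Radiographic response follows the criteria summarised in Protocol Appendix 2, and the 50% and 90% PSA reductions are written into Protocol 11.5.2. The LOH split has no such definition.

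An undefined cut also has a second cost. The study is open-label (Protocol 7.5) and SAP 11.3 plans no multiplicity adjustment. If the cut were settled after response is known, the best-looking split would exaggerate the association. Protocol 11.5.3.3 allows plasma and tumour samples to be used for developing a diagnostic test, so a spurious threshold could be carried forward.

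**Working it through.** **1. Inputs from the documents.** The score is a percentage and the protocol form is binary, with no cut-point (Protocol 11.5.3.5). The SAP form is unspecified (SAP 10.3.6). The illustrative n = 83 and 35% response rate are the Cohort A (BRCA1/2) design figures (Protocol Synopsis, statistical methods).

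**2. Inputs assumed, not in the documents.** %LOH is normally distributed and standardised, the effect is log-linear with an odds ratio (OR) per SD of 1.5 to 2.5, the test is two-sided at 5%, and the cut position is varied.

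**3. The plan's own figure for n = 83.** The probability of rejecting is the sum over x = 9 to 37 of P(X1 = x) × P(X2 ≥ 23 − x), with X1 ~ Bin(37, p) and X2 ~ Bin(46, p). At p = 0.20 this is 0.0487 and at p = 0.35 it is 0.9009. The stated 5% and 90% reproduce. They describe the primary efficacy test; the documents give no power for LOH.

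**4. Approximate effect of a cut.** Cutting a normal score at c, with a fraction q above it, multiplies the test's noncentrality by φ(c)/√(q(1 − q)). At the median this is 0.399/0.5 = 0.798. The information retained is 0.798² = 0.637, so 83 patients carry about as much as 0.637 × 83 = 53.

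For OR 2.0, the continuous noncentrality is ln(2) × √(83 × 0.35 × 0.65) = 0.693 × 4.345 = 3.01, and power is Φ(3.01 − 1.96) = 0.85. After a median split it is 3.01 × 0.798 = 2.40, and power is Φ(0.44) = 0.67. The loss is about 18 points.

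**5. Simulation** (20,000 replicates, score test, n = 83, 35% response). With no association the tests reject close to 5% of the time (0.049 to 0.050).

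| OR per SD | Continuous | Median split | Top-quarter split |
|---|---|---|---|
| 1.5 | 0.40 | 0.27 | 0.27 |
| 2.0 | 0.81 | 0.62 | 0.60 |
| 2.5 | 0.95 | 0.83 | 0.79 |

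Power lost over OR 1.5 to 2.5, in percentage points:

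| Setting | Median | Top third | Top quarter |
|---|---|---|---|
| n = 83, 35% response | 12.5–19.1 | 11.9–18.7 | 13.6–21.7 |
| n = 50, 35% response | 7.2–18.2 | 7.4–18.8 | 8.1–21.2 |

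**6. Sensitivity.** At n = 40 the loss is 5.5–18.1 points (median) or 5.7–20.6 (top quarter). At n = 83 with 20% response it is 9.5–20.6 or 7.2–17.6; with 45% response, 11.7–19.1 or 16.1–25.4. More extreme cuts cost more: at n = 83 and 35% response, a top-tenth cut loses 19.7–37.4.

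**7. If the truth is a step** (n = 83). With response 25% below and 50% above the median, a split exactly there has power 0.65 against 0.47 for the continuous test. With the step at the top quarter, it is 0.57 against 0.35. With 20% and 50% response the pairs are 0.84 against 0.65 and 0.74 against 0.50. The split gains about 19 to 24 points.

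A misplaced cut can lose. In a separate run with a 25%/50% step at the median, the continuous test had 49%, a top-third cut 39% and a top-quarter cut 29%. A nearby cut can still win: with the step at the top quarter, a top-third cut gave 40% against 35%.

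**8. If the cut is chosen after response is seen.** With no association, 35% response and the best-looking cut tested at a nominal 5%, searching the middle half of the scores gives false positives in 26% (n = 50) and 27% (n = 83). Searching from the 10th to the 90th percentile gives 39% and 40%.

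**The case against.** The strongest reply is that the later and more detailed document no longer contains the rule. Protocol 11.1 defers further analysis detail to the SAP, and SAP 10.3.6 has no dichotomy, so a continuous model is already permitted. This stands in part. A reader might infer that the SAP keeps the binary rule or that %LOH will be analysed only as high versus low; the documents support neither. But permitting any form is not specifying one, and the protocol sentence is neither replaced nor listed as changed.

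Second, no LOH hypothesis, test or power was planned. A reader might take a loss of some 13 to 21 points at n = 83 as a property of this trial. It is not: 83 is the Cohort A (BRCA1/2) efficacy total, and the effect size, distribution and cut are assumptions. The loss can be smaller or larger, and it reverses for a step at the cut.

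Third, a high-LOH category exists in the programme. Protocol 3.5 describes BRCA-like ovarian tumours with high LOH, and Protocol 3.4.2 says the CO-338-017 ovarian study uses a prospectively defined genomic signature. A threshold effect is therefore plausible, which is a reason to keep a split as a secondary analysis. No numeric threshold is carried into this plan, so an undefined cut is still undefined.

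Finally, two inferences go too far. The documents do not say the cut will be chosen after response is seen; they leave its timing open. Nor can one conclude that no guideline supports a cut; the documents simply cite none.

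**Conclusion.** The point holds in a limited form. The protocol calls for a binary %LOH analysis without a cut-point, the SAP leaves the form open, and the difference is not recorded. Under a roughly log-linear effect, with the assumptions in the working and a cut between the median and the top quarter, dichotomising costs about 12 to 22 points of power at an illustrative n = 83 and about 7 to 21 at n = 50. The inflation from a cut chosen on the data is conditional on that being done. The primary and secondary analyses are unaffected, so the importance is low.

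**What to change.** In SAP 10.3.6, state text such as:

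> Response will be related to %LOH mainly as a continuous variable by logistic regression, reporting the odds ratio per SD with its 95% CI. Any high/low split is secondary, and is either fixed and justified before response data are examined or descriptive at the observed median.

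List this in SAP Section 13 as a change from Protocol 11.5.3.5, and align the protocol wording at the next amendment. An amendment for this alone is not needed, since amendments require ethics committee approval (Protocol 13.8).

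The cost is a short SAP edit and one logistic model on data already produced, with no extra patients, samples or procedures. The small downside is less direct comparability with high/low LOH classifications used elsewhere in the programme, which the secondary split preserves.
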